### 10.2. Method of analysis

#### Descriptive Analysis:

Basic demographic characteristics of the study population will be summarized using descriptive statistics such as mean, median, standard deviation for continuous variables, and frequencies or percentages for categorical variables.

#### Primary Outcome Analysis:

Positive and negative predictive values (PPV and NPV) of plasma PG levels in predicting a diagnosis of cancer will be calculated.

Receiver Operating Characteristic (ROC) curve analysis will be conducted to assess the discriminatory ability of plasma PG levels for cancer diagnosis. This includes calculating the area under the ROC curve (AUC).

Sensitivity, specificity, accuracy, and likelihood ratios will also be calculated to evaluate the diagnostic performance of plasma PG levels.

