Given that over 90% of patients referred to the lower GI cancer pathway will not have cancer, a screening test or tests to rule out cancers would reduce the burden on NHS targets and could be cost effective at excluding unnecessary tests. The most useful group to be tested and excluded from the pathway in the future would be those patients where the index of suspicion is low. These include those without a family history of CRC, ages between 18 and 55 (not yet eligible for CRC screening programme), no weight loss, good performance status of 0-1 and no history of inflammatory bowel disease.

Global CRC screening programs aim for a 65% participation rate, a target met in many European nations and reaching 74% in the USA. However, CRC screening lags behind breast and cervical cancer screening, which typically exceed 70% participation. A significant barrier to CRC screening is the low attendance rate for colonoscopy or CT colonography following abnormal faecal immunochemical tests (FIT) or faecal occult blood tests (FOBT), ranging from 10% to 30%. This low attendance is often attributed to negative experiences, word-of-mouth discussion, and sociocultural factors.

As emerging technologies like liquid biopsy, utilising biomarkers such as progastrin or transposable elements, offer potential for non-invasive CRC detection, understanding patient preferences for different screening modalities becomes crucial. These tests

vary in invasiveness, frequency, and risk profiles, and their effectiveness in altering risk profiles of CRC differs.

To optimise patient adherence and early detection, it is essential to identify the factors that influence patient choice among these diverse diagnostic options.

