# 6. Study objectives

#### 6.1. Primary objective

The primary objective of this study is to test whether plasma PG levels accurately predict the diagnosis of CRC and or polyps in a group of 2WW patients undergoing the standard investigations. The study will also aim to distinguish the absence of cancer by virtue of actual levels of plasma PG. To determine the sensitivity and specificity of plasma PG levels in patients with colorectal cancer (CRC), and benign colonic polyps when investigated via a 2WW referral pathway

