#### 6.4. Primary endpoint

The accuracy of plasma PG levels to predict a cancer diagnosis in a 2WW referral cohort. Positive and negative predictive values along with the relevant Receiver Operator Characteristic (ROC) curve will be calculated and plotted for patients with confirmed cancer and benign polyp diagnoses.

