Patients will be screened for suitability and recruited to the study within the 2WW clinic. Upon the receipt of informed consent, patients' medical history and a blood sample will be taken. This includes initials, date of birth, sex, BMI, ethnicity, height, and weight, to be recorded on the CRF. The blood sample will be transported to and processed to extract the plasma and stored in the laboratories at the Blizard Institute based at the NBRC, [name]. Batches of 100 fully anonymised plasma samples will be sent to Progastrin Manufacturing, Biodena Care, [name] for the plasma progastrin assay. The remaining unused plasma will be stored in Blizard Institute, Whitechapel, London lab and will be used for RNAseq analysis for transcript signatures to identify potential transposable elements and nanopore DNAseq to provide sequence variants and epigenetic modifications of DNA. The latter assay's will be conducted at the Blizard Institute laboratories.

The plasma progastrin levels will be sent back to the study team at Queen Mary University of London based at the NBRC, [name] by the Progastrin Manufacturing team, Biodena Care [name], [name] and will be added to the study database. Participants are free to withdraw from the study at any time and will be provided with reassurance that this will not affect their care in any way.

Before enrolment into the study, participants will be fully informed of the nature of the study and all relevant aspects of study procedures. It is the investigators' responsibility to explain the nature of the study, its purpose and associated procedures, the expected duration and the potential benefits and risks of participation to each subject prior to their entry into the study (i.e. before examinations and procedures associated with selection for the study are performed).

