#### 10.1. Sample size

Approximate Annual Referral Volume for RLH ≈ 2400 patients per year Recruitment Period:18 weeks (4-5 months)

Eligible Patients:

18 weeks \* (2400 patients/year / 52 weeks ) ≈ 831 eligible patients

Screen Failure:

30% screen failure rate

Potentially 70% of eligible patients enter the study: 831 \* 0.7 ≈ 582 patients

Case and Control Allocation:

Based on cancer office for LGI approximately 9.5% of lower GI patients have a cancer hence:

Cases: 9.5% of 582 ≈ 55 patients with LGI cancer

Controls: (100-9.5)% of 582 ≈ 527 patients without LGI cancer - assuming no other

cancers are detected

Plasma biomarkers in stratifying patients referred via the lower gastro-intestinal (LGI) suspected cancer two-week wait (2WW) pathway

V5 7th of April 2025

Sensitivity and Specificity of PG:

The sensitivity of the PG test is estimated to be between 70% and 87% at a cutoff of 0.2 pM. The specificity of the test at this cutoff is 97.5%.

Statistical Power and Significance Level:

To ensure adequate statistical power, we aim to achieve a power of 0.8 and a significance level of 0.05.

Receiver Operating Characteristic (ROC) Curve Analysis:

A power calculation was performed using the pROC package in R. The following parameters were used:

Number of cases (GI cancer): 55 Number of controls (no cancer): 527 Area under the curve (AUC): 0.6118569

Power = 0.8

To address the secondary outcome of the study a random number of 100 samples out of 582 number of samples (25 LGI cancer proven samples and 75 non-cancer (normal) samples) will be selected and tested for TEs in order to identify and validate novel biomarkers as potential tests for colorectal cancer diagnosis

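### Are the primary PPV and NPV undefined because sections 6.4 and 10.2 name no progastrin cut-off?

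*Protocol*

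**What the plan says.** Section 6.4 defines the primary endpoint as the accuracy of plasma PG levels for a cancer diagnosis and adds: "Positive and negative predictive values along with the relevant Receiver Operator Characteristic (ROC) curve will be calculated and plotted", for confirmed cancers and for benign polyps. Section 10.2 repeats this ("Positive and negative predictive values (PPV and NPV) of plasma PG levels in predicting a diagnosis of cancer will be calculated"), adds ROC analysis with the AUC, and continues: "Sensitivity, specificity, accuracy, and likelihood ratios will also be calculated to evaluate the diagnostic performance of plasma PG levels". Neither section gives a cut-off or a rule for choosing one.

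The laboratory reports a quantity: "The plasma progastrin levels will be sent back to the study team" (section 9), measured by ELISA (section 14.3).

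One cut-off appears in the protocol, in section 10.1: "The sensitivity of the PG test is estimated to be between 70% and 87% at a cutoff of 0.2 pM", followed by "The specificity of the test at this cutoff is 97.5" (per cent). The power calculation in the same section uses 55 cases, 527 controls and an AUC of 0.6118569. It does not use the cut-off.

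**The concern.** Apart from the ROC curve and its area, every measure listed for the primary outcome requires each patient to be called positive or negative. Without a stated threshold, the primary PPV and NPV are not single defined quantities, because the same data give different values at different cut-offs.

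The study's aims also point in two directions. Predicting cancer favours a high-specificity cut-off such as 0.2 pM. Section 6.1 adds a rule-out aim ("The study will also aim to distinguish the absence of cancer by virtue of actual levels of plasma PG"), and section 5.1 gives the motive for it ("a screening test or tests to rule out cancers would reduce the burden on NHS targets"). Ruling out favours a lower cut-off. A reader could therefore fear that the threshold will be chosen after the ROC curve has been seen, from the same 55 or so cancers, and that the resulting accuracy will be flattering.

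**Working it through.** **1. The plan's own figure.** The test is AUC against 0.5 with the Obuchowski binormal variance (assumed to be the formula behind the software named in 10.1), two-sided alpha 0.05, and κ = 527/55 = 9.58.

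- A = 1.414 × z(0.6118569) = 0.4018
- V = 0.0099·exp(−A²/2)·[(5A² + 8) + (A² + 8)/κ] = 0.0882
- z(power) = [√55 × 0.1118569 − 1.960 × √(0.0792 × (1 + 1/κ))] / √V = (0.8296 − 0.5797)/0.2970 = 0.841
- Power = 0.80

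The stated power reproduces, and no cut-off enters it.

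**2. Accuracy at 0.2 pM from the protocol's inputs** (55 cancers, 527 controls, specificity 97.5%).

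- False positives: 0.025 × 527 = 13.2
- Sensitivity 70%: true positives 38.5, PPV = 38.5/(38.5 + 13.2) = 74.5%, NPV = 513.8/(513.8 + 16.5) = 96.9%
- Sensitivity 87%: true positives 47.85, PPV = 47.85/(47.85 + 13.2) = 78.4%, NPV = 513.8/(513.8 + 7.15) = 98.6%

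So 10.1 already implies definite values for every measure listed in 10.2.

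**3. How far the cut-off moves the results.** Assumption: controls N(0, 1) and cases with SD r, on a curve through 70% sensitivity at 97.5% specificity. The case mean is then 1.960 + r × 0.524. PPV and NPV follow from Bayes' rule at 9.5% prevalence. For r = 1:

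| Cut-off | Sensitivity | Specificity | PPV | NPV | Missed of 55 | False positives of 527 |
|---|---|---|---|---|---|---|
| 0.2 pM | 70% | 97.5% | 74.6% | 96.9% | 16.5 | 13 |
| Youden | 89.3% | 89.3% | 46.7% | 98.8% | 6 | 56 |
| 53/55 detected | 96.4% | 75.5% | 29.2% | 99.5% | 2 | 129 |

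(At 0.2 pM, 74.6% uses a prevalence of exactly 9.5%. The 74.5% in step 2 uses 55/582.)

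For r from 0.8 to 2.0, the Youden PPV is 47–52% with about 4–12 cancers missed. At 53/55 sensitivity, PPV is 12–37% with about 91–379 false positives. The counts in the table are therefore one scenario in a wide range. On all these curves NPV stays between 96.9% and 99.5%. With 87% sensitivity at 0.2 pM, PPV is about 78% there, 61–69% at Youden and 28–57% at 53/55.

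The spread depends on the AUC. Moving specificity from 50% to 97.5% (equal variances, prevalence 55/582):

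- AUC 0.612: PPV 12.0% to 19.9%, NPV 93.3% to 90.9%
- AUC 0.90: PPV 16.8% to 64.8%, NPV 99.3% to 94.4%

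**4. Bias if the cut-off were taken from the same patients.** Simulation of 55 cases and 527 controls, 10,000 replicates, equal variances, empirical Youden cut-off. Optimism is apparent minus true value at the chosen cut-off, in percentage points:

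| AUC | Sensitivity | PPV | NPV |
|---|---|---|---|
| 0.612 | 6.6 | 1.8 | 1.2 |
| 0.70 | 5.8 | 1.7 | 0.9 |
| 0.84 | 4.7 | 1.7 | 0.6 |
| 0.9605 | 3.4 | 1.8 | 0.4 |
| 0.985 | 2.7 | 1.9 | 0.3 |

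Sampling error at 0.2 pM, as exact 95% intervals on whole-number counts with 70% sensitivity: PPV 38/51, 60–86%; NPV 514/531, 95–98%. The optimism in PPV and NPV is smaller than either interval's half-width.

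**The case for a change.** The best case for a change is that a positivity threshold is part of the endpoint, because it decides what a positive test is. On that view it belongs in the protocol and should not wait for an analysis plan. The protocol cites a cut-off and then does not say whether it governs the endpoint. The rule-out aim makes a lower threshold a real alternative, and under the assumed curve PPV can differ between the two by tens of points, more than its sampling interval. Fixing this would take a sentence in each of two sections.

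Much of that is factually right. Sections 6.4 and 10.2 are silent, 0.2 pM occurs once, and PPV is sensitive to the choice. Section 6.4 also does not say whether the same cut-off would serve the benign-polyp figures. An explicit sentence would be good practice.

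It does not show an error. Section 10.1 describes the PG test by its sensitivity and specificity at 0.2 pM, section 8.2 describes the assay as a commercial product, and no competing threshold appears anywhere. The natural reading is that the accuracy measures are taken at 0.2 pM. The rule-out aim can be read from the ROC curve, which the plan reports in any case. That a threshold would be picked after the fact is inferred from silence; the protocol does not say so.

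**Conclusion.** The gap is real, but it is missing detail that an analyst can fill sensibly from section 10.1, and a rule for dichotomising PG may be set out in an analysis plan not available here. No printed number or rule is wrong. The sample size and the reproduced power of 0.80 rest on the AUC and are untouched. The protocol calls the study a pilot and a feasibility study, and no success criterion is attached to PPV or NPV.

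The consequences are uneven. PPV depends strongly on the cut-off: about 75% at 0.2 pM against 47–52% at the Youden point, on binormal curves through 70% sensitivity and 97.5% specificity. NPV moves by under 3 points on those curves, and by about 5 points (94.4% to 99.3%) if the AUC is 0.90 and specificity runs from 97.5% down to 50%. Optimism from a same-data cut-off would be 2.7–6.6 points for sensitivity, under 2 for PPV and about 1 or less for NPV. All of this assumes normally distributed markers. Section 5.1 describes PG as undetectable in healthy people; if many values lie at the detection limit, the lower cut-offs may not be attainable. No change to the plan follows.

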#### Secondary Outcome Analysis:

#### Subgroup Analysis:

Subgroup analysis may be performed to assess whether the predictive ability of plasma PG levels varies across different patient subgroups (e.g., age, sex, referral pathway).

Statistical Testing:

Plasma biomarkers in stratifying patients referred via the lower gastro-intestinal (LGI) suspected cancer two-week wait (2WW) pathway

Depending on the nature of the data and research questions, appropriate statistical tests may be conducted. For example, t-tests or Mann-Whitney U tests for continuous variables and chi-square tests or Fisher's exact tests for categorical variables.

#### Survival Analysis (if applicable):

If assessing time-to-event outcomes (e.g., time until cancer diagnosis), survival analysis techniques such as Kaplan-Meier curves and Cox proportional hazards models may be utilized.

#### Multivariate Analysis (if applicable):

If relevant covariates are identified, multivariate regression analysis may be conducted to assess the independent association between plasma PG levels and cancer diagnosis while adjusting for potential confounders.

#### Sensitivity Analysis:

Sensitivity analysis may be performed to assess the robustness of the results to variations in assumptions or analytical methods.

# Qualitative Analysis (if applicable):

If qualitative data are collected (e.g., patient experiences or perspectives), thematic analysis or other appropriate qualitative methods may be employed to extract themes and insights.

#### Ethical Considerations:

Throughout the analysis, ethical considerations regarding patient confidentiality, consent, and privacy will be strictly adhered to, ensuring compliance with ethical guidelines and regulations.

#### 11. Ethics

REC and HRA approval will be sought from

Recruitment will take place in 2WW and STT (virtual and face-to-face) outpatient clinics at Barts Health NHS Trust. Informed consent will be sought through a conversation, printed information, and a consent form.

#### Confidentiality

The study will be conducted in accordance with the principles of the Declaration of Helsinki (Ethical Principles for Medical Research Involving Human Subjects).

The Protocol, questionnaires, Consent Forms and Patient Information Sheet will be submitted to a National Research Ethics Service (NRES) approved Research Ethics Committee before patients are recruited and patients are enrolled. The Investigators will receive all the documentation needed for submitting the present Protocol to the Ethics Committee. No study activities will be initiated until the written approval of that Committee is received. A copy of the respective approval letters will be transmitted to

Plasma biomarkers in stratifying patients referred via the lower gastro-intestinal (LGI) suspected cancer two-week wait (2WW) pathway

V5 7th of April 2025

the Sponsor before starting the study. If approval is suspended or terminated by the Ethics Committee, the Investigator will notify the Sponsor immediately.

It is the responsibility of the Chief Investigator to report study progress to the Ethics Committee as required or at intervals not greater than one year. The Chief Investigator will be responsible for reporting any serious adverse events to the Ethics Committee as soon as possible and in any event within 72 hours.

#### 11.1. Annual Safety Reporting

All day-to-day management of the study will be the responsibility of [name] (CI). The co-investigators, especially the Research Fellow ([name]) will also be involved in the day-to-day operations of the study. The study team will meet every two months to discuss, the study progress and the findings. These meetings will review and ensure all the study materials are up-to-date, and all the team members are fully trained to undertake the research activities (GCP trained). Formal minutes will be kept for these meetings. Due to the low-risk nature of the study, there will be no data monitoring and ethics committee (DMEC). The trial may be prematurely discontinued due to a lack of recruitment, and the CI will advise on whether to continue or discontinue the study and make a recommendation to the sponsor. There will be no formal stopping rules based on the intervention outcomes.

#### 12. Public Involvement

Patients worked with the Chief Investigator, [name], to design and develop the research as well as this application and will be involved in the delivery and dissemination. PPIE members are equal partners in the research.

[name], a 2WW patient, is a named contact on this application and is joined by four members of the After Bowel Cancer PPIE group who represent some of the diverse patient populations in east London in terms of ethnicity, gender, SEC, age, religion, sexuality, as well as nationalities and languages spoken. These PPIE representatives will join the project events.

We believe that the level and quality of the partnership between PPIE members and clinical research staff is a model of involvement and engagement and hope to co-author publications and deliver public talks about this strength, as a means of encouraging an ecosystem of best practice in QMUL, Barts Health, and beyond.

# 13. Data handling and record keeping

#### 13.1. Data management

The use and control of all data will comply at all times with the requirements of the Data Protection Act. All data management procedures will be detailed and referred to as the Data Management Plan.

Plasma biomarkers in stratifying patients referred via the lower gastro-intestinal (LGI) suspected cancer two-week wait (2WW) pathway

In summary; the data collected during the trial will be a combination of clinical data – 2WW referral symptoms, age, gender, history of cancers and other GI diseases (e.g. inflammatory bowel disease), investigation-related including any diagnosis of cancers), progastrin assay results and final outcome from the 2WW referral episode. Most of the data will be recorded straight on CRF's and routine data that can be verified with the medical notes. All data will be entered and checked by a designated researcher. The database will be designed and built by the research team on REDCap data system and will be uploaded onto a dedicated folder on the secure virtualised environment at the Barts Cancer Centre (BCC). The BCC environment requires dual factor authentication to access the portal and the folders where the data are stored are only accessible to the appropriate members of the study team.

The Case Report Forms (CRFs) will be solely for the use of researchers to facilitate data collection as per protocol before it is transcribed onto the REDCap database. The CRF documents contain the Participant ID, study name, site number/ID, researcher name, (where appropriate), CRF document name and other relevant information on each page and space to record appropriate signatures.

In accordance with its current Records Retention Schedule, research data will be retained by the sponsor, Queen Mary University of London for 5 years after the research has ended. Access to stored records is strictly controlled.

For trials involving Barts Health NHS Trust patients, undertaken by Trust staff, or sponsored by BH or QMUL, the approved repository for long-term storage of local records is the Trust Modern Records Centre.

#### 13.2. Source Data

The study team will work closely with staff at the participating site(s) to ensure accurate (complete, valid and reliable) collection of data. Appropriate data validation will be incorporated into the eCRF. The site PI is responsible for ensuring that all data queries are resolved. Ongoing data entry, validation at adherence to the trial protocol at sites will be closely monitored by the study team and any concerns will be raised to the CI. A data management plan will cover all aspects of managing the data such as, the CRF design, the data management system for data collected, data entry, data handling processes including data checking, query management and cleaning, data transfer, quality control procedures, processes for interim and final data extractions, the procedures for freezing and locking the databases.

#### 13.3. Confidentiality

The CRFs will be anonymised and study data will not be linked to individual patients other than by those authorised to have access and not in any publication of results. The CRF to be used for the study consists of pages that contain within the header or footer the protocol number, subject initials, subject number and other relevant information. It is composed of an introductory section for the selection and inclusion of participants in the study and a section for the assessment period. Contained within

the treatment period section are the forms for registration of possible adverse events and for any suspension of the study.

All CRFs will be completed using a ball-point pen with black ink. All unused CRFs for dropouts must be retained and will be made available to the Sponsor for inspection at any site visit.

All requested information must be entered on the CRFs. If an item is not available or is not applicable, this fact should be indicated; there should be no blank spaces.

Corrections should be made by striking through the incorrect entry with a single line and by entering the correct information adjacent to it. The correction must be initialled and dated by an Investigator or a designated qualified individual. Each set of completed CRFs must be reviewed, signed and dated by an Investigator.

The use and control of all data will comply at all times with the requirements of the Data Protection Act 2018. The PI of the study will register with the local Data Protection Officer. All data management procedures will be detailed and referred to as the Data Management Plan.

The database will be designed and built by the research team on QMUL approved REDCap data system within the Barts Cancer Centre virtual environment. All study data will be uploaded onto a dedicated folder on the secure virtualised environment at the Barts Cancer Centre (BCC) which holds the REDCap system. Appropriate CRFs will be prepared for the collection of the data requested by the protocol. All response variables will be entered into the database by the data management personnel.

